A real-world study comparing the efficacy of different treatment options for early missed miscarriage.

Funding source: None

Research Institution: Xiangya Third Hospital, Central South University

Research Leader: [name]

Version number: 1.0

Version date: 2023.11.21

A handwritten signature in black ink, appearing to be '[name]' ([name]), the research leader.

Table of contents

Research Proposal Summary	3
Research Text	6
1. Research Background	6
2. Research Objectives	7
3. Research Design	8
4. Research Content	10
5. Key Evaluation Indicators	16
6. Safety considerations	17
7. Statistical Analysis	17
8. Data integrity and quality assurance	18
9. Ethical Statement	18
10. References	18

Research Proposal Summary

Experiment title:

A real-world study comparing the efficacy of different treatment options for early missed miscarriage.

Research objective:

Currently, there is no unified standard for the treatment of missed abortion in clinical practice. This study aims to collect clinical data on this type of disease to compare the differences in efficacy of different treatments. Based on this, it will also explore the synergistic effect of combining different doses of estrogen with medical induction of labor, conduct statistical analysis on the efficacy, and evaluate whether the treatment plan achieves the desired therapeutic effect while reducing the occurrence of complications, thus providing a valid basis for the subsequent clinical treatment of missed abortion.

Experimental Design:

This study is divided into two parts. The first part is a retrospective analysis, which explores the differences in clinical efficacy and reproductive outcomes between surgical and medical treatment for missed abortion. The second part is a prospective study, which explores the impact of different doses of estrogen combined with surgical or medical abortion on the efficacy of early pregnancy missed abortion, and seeks the optimal clinical treatment method for missed abortion .

Experimental procedure:

The retrospective analysis included patients diagnosed with missed abortion by ultrasound at our outpatient clinic from January 2018 to March 2023. Patients meeting both inclusion and exclusion criteria were consecutively enrolled. The prospective study included patients diagnosed with missed abortion by ultrasound at our outpatient clinic from December 2023 to December 2024. Patients meeting both inclusion and exclusion criteria were consecutively enrolled. General information was collected from patients in different groups, including gestational age at termination of pregnancy, symptoms, ultrasound findings of uterine size, gestational

sac size and location, serum HCG levels, parity, and whether there were other intrauterine diseases before pregnancy. Patients were grouped according to their wishes and underwent either drug or surgical treatment. Surgical time, intraoperative blood loss, type and dosage of medications, time of gestational sac expulsion, amount of vaginal bleeding, and adverse drug reactions were recorded. Follow-up included the duration and amount of vaginal bleeding after discharge, time of menstrual resumption, changes in menstrual flow, and the probability and outcome of subsequent pregnancies.

Selection criteria:

1. Retrospective analysis : Patients diagnosed with missed abortion by ultrasound at our outpatient clinic from January 2018 to March 2023 who met the inclusion criteria but did not meet the exclusion criteria were enrolled consecutively.

2. Prospective study: Patients diagnosed with missed abortion by ultrasound at our outpatient clinic from December 2023 to December 2024 who met the inclusion criteria but did not meet the exclusion criteria were enrolled consecutively.

Inclusion criteria:

① Age 18-40 years ; ② Diagnosed with early pregnancy missed abortion by imaging and laboratory examinations; ③ All indicators of routine examinations before treatment are within the normal range, and there are no serious systemic diseases; ④ No indication for emergency curettage ; ⑤ Good compliance, and follow-up observation as required (prospective study).

Exclusion criteria:

① Those with contraindications to medical abortion; ② Those allergic to estrogen or with contraindications to estrogen use; ③ Those unable to follow up according to the follow-up plan; ④ Those with thromboembolic diseases, known or suspected breast cancer, hormone-dependent tumors, etc.; ⑤ Those with vaginal bleeding exceeding the usual menstrual flow; ⑥ Those with serious heart, liver, or kidney diseases; ⑦ Those with serious internal or surgical diseases, malignant

tumors, or mental illnesses who cannot cooperate.

Statistical methods:

using SPSS 26.0 statistical software. Quantitative data were expressed as mean \pm standard deviation, and the independent t-test was used for comparisons between groups. Count data were expressed as percentages (%), and the chi-square test was used for comparisons between groups. The rank-sum test was used for comparisons between groups of ordinal data. $P < 0.05$ was considered statistically significant.

Research Text

1. Research Background

Missed abortion in early pregnancy refers to a pregnancy of ≤ 12 weeks in which the embryo or fetus has died and remains in the uterine cavity without being expelled naturally in time [1]. The most common cause of missed abortion is chromosomal abnormalities, followed by immune factors, endocrine disorders, uterine abnormalities, hereditary thrombosis, infection, environmental factors [2], lifestyle habits [3]. Currently, there are three main treatment methods for missed abortion in early pregnancy: expectant management, drug therapy, and surgical treatment [4]. The effectiveness of the three treatment methods is 58%, 81%, and 96%, respectively [5]. Previous views held that when missed abortion occurs, the embryo or fetus in the uterus fails to be expelled from the body in time, and the embryonic organization site adheres tightly to the uterine wall, which is not easy to separate. This can cause complications such as endometrial damage, intrauterine adhesions, menstrual disorders, and infertility. If the pregnancy tissue stays in the uterine cavity for a longer time, it can also lead to tissue dissolution and release a large amount of hemolysin into the pregnant woman's blood circulation, causing coagulation dysfunction, resulting in massive bleeding, or even disseminated intravascular coagulation [6]. Therefore, when the diagnosis of early missed abortion is clear, surgical intervention is often used to terminate the pregnancy. However, the risk of abortion surgery depends on the tightness of the adhesion between the embryonic organization site and the uterine wall, the size of the gestational sac, the clinical situation, the surgical environment, the professional level of the surgeon, and the available surgical instruments and equipment. It may produce surgical complications of varying degrees, such as cervical injury, uterine perforation, intraoperative and postoperative infection, intrauterine adhesions, and incomplete abortion, which may affect subsequent pregnancies and pregnancy outcomes. In addition to surgical treatment, the medical abortion regimen of mifepristone combined with misoprostol has been used clinically for more than 20 years and has been proven to be safe and effective for terminating early pregnancy [7]. Moreover, if medical

abortion is used first to completely expel the pregnancy tissue, subsequent curettage can be avoided. Regarding the use of estrogen therapy in combination with medical abortion, studies have shown that estrogen can significantly stimulate the proliferation and differentiation of endometrial stem cells, and this effect is dose-dependent. Physiological doses of estrogen promote the differentiation of endometrial stem cells and maintain the existing thickness of the endometrium; supraphysiological doses of estrogen can promote the proliferation of endometrial stem cells and promote the thickening of the endometrium. [8]. Other reports indicate that mifepristone can reduce chorionic villus activity by decreasing the content of estrogen and progesterone receptors in the decidual tissue. This leads to a decrease in estrogen receptor levels in the early pregnancy decidua, preventing estrogen from exerting its biological effects, affecting the repair of the endometrial wound after medical abortion, and causing a decrease in the sensitivity of uterine smooth muscle to oxytocin, preventing the decidua from being easily expelled and thus leaving residues in the uterine cavity. Conventional doses of exogenous estrogen often fail to restore the endometrium to an ideal state after medical abortion. Therefore, combining medical abortion with high-dose estrogen may improve the effectiveness of medical induction, reduce vaginal bleeding, and promote endometrial repair. However, in current clinical practice, there is still a lack of clinical efficacy studies on the application of high-dose estrogen in the treatment of missed abortion in early pregnancy. This study aims to evaluate the efficacy of different treatment methods for missed abortion in early pregnancy and further explore whether the treatment regimen of mifepristone combined with misoprostol and high-dose estrogen can achieve ideal efficacy and reduce the occurrence of complications, providing a valid basis for the subsequent clinical treatment of missed abortion.

2. Research Objectives

Currently, there is no unified standard for the treatment of missed abortion in clinical practice. This study aims to collect clinical data on this type of disease to compare the differences in efficacy of different treatments. Based on this, it will also explore the synergistic effect of combining different doses of estrogen with medical induction of

[figure not shown]
labor, conduct statistical analysis on the efficacy, and evaluate whether the treatment plan achieves the desired therapeutic effect while reducing the occurrence of complications, thus providing a valid basis for the subsequent clinical treatment of missed abortion.

3. Research Design

Sample size calculation: Retrospective study of 400 cases

A prospective study of 180 cases

flow chart:

4. Research Content

This study is divided into two parts. The first part is a retrospective analysis to explore the differences in efficacy and fertility outcomes among patients with different treatment methods for missed abortion; the second part is a prospective study to explore the impact of different doses of estrogen combined with different treatment methods on the efficacy of treatment for missed abortion in early pregnancy.

Part I retrospective analysis collected data from patients with early pregnancy loss due to miscarriage who visited the Department of Gynecology at Xiangya Third Hospital of Central South University between January 2018 and March 2023. All patients had voluntarily accepted drug or surgical treatment and signed relevant treatment consent forms, and were exempted from signing informed consent forms regarding the data collection.

Part II, a prospective study, collected data from patients with early pregnancy loss due to miscarriage who visited the Department of Gynecology at Xiangya Third Hospital of Central South University between December 2023 and December 2024. All patients received either medication or surgical treatment at their own discretion. All participants were required to provide fully informed consent and sign an informed consent form.

Selection criteria:

① Age 18-40 years ; ② Diagnosed with early pregnancy missed abortion by imaging and laboratory examinations; ③ All indicators of routine examinations before treatment are within the normal range, and there are no serious systemic diseases; ④ No indication for emergency curettage ; ⑤ Good compliance, and follow-up observation as required (prospective study).

Exclusion criteria:

① Those with contraindications to medical abortion; ② Those allergic to estrogen or with contraindications to estrogen use; ③ Those unable to follow up according to the follow-up plan; ④ Those with thromboembolic diseases, known or suspected breast cancer, hormone-dependent tumors, etc.; ⑤ Those with vaginal bleeding exceeding the

usual menstrual flow; ⑥ Those with serious heart, liver, or kidney diseases; ⑦ Those with serious internal or surgical diseases, malignant tumors, or mental illnesses who cannot cooperate.

4. Research Process

Grouping:

1. Retrospective analysis: Based on the different treatment methods for patients with early missed abortion, patients were divided into a drug treatment group and a surgical treatment group.

2. Prospective study: Patients with early missed abortions were grouped according to their own wishes to choose surgical or medical abortion, and to the use of different doses of estrogen before and after abortion treatment .

This study did not intervene in patient treatment; it only pre-designed and collected relevant data. No additional examinations or tests were performed on patients during the study, and all procedures were conducted according to standard clinical practice. After treatment, patients were divided into surgical and drug treatment groups based on their chosen treatment plans. Furthermore, based on the estrogen dosage chosen by the patients, they were divided into non-stimulatory estrogen, standard-dose estrogen, and high-dose estrogen groups. Data were then statistically analyzed.

Timing of treatment :

The following criteria are considered indicative of missed abortion in early pregnancy: Ultrasound diagnosis of missed abortion includes: ① Crown-rump length $\geq 7\text{mm}$, no fetal heartbeat detected. ② Average diameter of the gestational sac in the uterine cavity $\geq 25\text{mm}$, no embryo detected. ③ No yolk sac seen in the uterine cavity, and no embryo or fetal heartbeat detected after 2 weeks. ④ Yolk sac visible in the uterine cavity, and no fetal heartbeat detected after 11 days.

Treatment methods:

1. Retrospective Analysis: Patients diagnosed with early pregnancy loss at our hospital between January 2018 and March 2023 were included in this study. All patients were

informed of the available treatment options and associated risks before treatment and signed a treatment consent form. Patients were grouped according to their preferred treatment method: medication or surgery.

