For all patients with missed abortions, treatment to promote uterine contraction after the expulsion of the pregnancy tissue includes: routine intravenous administration of uterotonic agents (oxytocin is commonly used , and ergonovine may be used if

necessary) ; and oral administration of uterotonic drugs (such as Wujia Shenghua capsules) for 2 weeks. Infection prevention: If signs of infection or high-risk factors for infection are present, antibiotics may be used as appropriate, and the type, route of administration, dosage, frequency, and duration of administration of antibiotics must be accurately recorded. Pathological examination: The pregnancy tissue expelled during the procedure is routinely sent for pathological examination; chromosomal analysis of the abortion tissue is performed based on the patient's preference.

End of treatment sign:

(1) A follow-up ultrasound showed no retained products of conception, and serum HCG levels returned to normal; (2) Patients with retained products of conception underwent clinical observation or curettage.

5. Key Evaluation Indicators

(1) Evaluation indicators before treatment: patient's age, time of consultation, gestational week of termination of pregnancy, symptoms, ultrasound findings of uterine size, gestational sac size and location, serum HCG level, parity , number of previous intrauterine procedures, and whether there are other intrauterine diseases before pregnancy (such as intrauterine adhesions, uterine septum , submucosal fibroids).

(2) Routine examination data after admission: routine vaginal discharge test, HPV/TCT, routine blood tests, liver and kidney function tests, electrolyte test , coagulation function test, thyroid function test, blood β -HCG test, anti-Müllerian hormone test, pre-transfusion examination, electrocardiogram, chest X-ray, uterine and bilateral adnexa 2-D/3-D color Doppler ultrasound and other related examinations.

(3) During drug treatment: the type and dosage of drugs taken, the time of expulsion of the gestational sac, the amount of vaginal bleeding, adverse drug reactions, etc.

(4) Surgical data: Date of surgery; depth of uterus; location and size of the gestational tract; operation time (from the start of the distension procedure to the withdrawal of the endoscope); amount of intraoperative blood loss; whether there is any retained gestational tract after surgery; clarity of the intraoperative field of vision;

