volume of distension fluid in and out; whether there is a decrease in blood oxygen saturation; whether complications such as uterine perforation, acute left heart failure, or gas embolism occur. Postoperative follow-up data : serum β -HCG, complete blood count, CRP, procalcitonin (not necessary), ultrasound to check for retained gestational tract, and if so, record the maximum diameter of the retained tract.

(5) Outpatient follow-up data 3 months after treatment : duration of vaginal bleeding after miscarriage, amount of bleeding, time of menstruation resumption , changes in menstrual flow , whether ultrasound indicates intrauterine adhesions, condition of endometrium, whether intrauterine adhesion surgery was performed, and intrauterine adhesion score.

(6) Pregnancy outcomes: Pregnancy rate after 1 year of trying to conceive (followed up every 6 months) ; spontaneous abortion rate, premature birth rate, full-term birth rate, stillbirth rate in subsequent pregnancies.

Follow-up data is used only for clinical efficacy evaluation.

6. Safety considerations

The data in this study are derived from clinical data and are absolutely safe. The use of estrogen for missed abortion is in accordance with routine clinical treatment, with the standard dose being 2 mg. 4 mg of estrogen is an off-standard dose, but numerous domestic and international studies have shown that high-dose estrogen for women of childbearing age without contraindications to estrogen use can effectively improve patients' clinical symptoms and has a high safety profile.

7. Statistical Analysis

using SPSS 26.0 software. Normally distributed measurement data were expressed as ($\bar{x} \pm s$), and t-tests were used for comparisons between two groups, while ANOVA was used for comparisons among multiple groups. Non- normally distributed measurement data were expressed as the median, and a nonparametric rank-sum test was used . Categorical data were analyzed using the χ^2 test or Fisher 's test. $P < 0.05$ was considered statistically significant.

8. Data integrity and quality assurance

Researchers should ensure that data is authentic, accurate, complete, and traceable, and should ensure the integrity of basic clinical research documents during retention, avoiding intentional or unintentional alteration or loss.

9. Ethical Statement

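### The 1-year pregnancy rate is compared between self-chosen groups, but infertility history and mode of conception of the index pregnancy are on neither pre-treatment list, so a pre-existing difference could be taken for a treatment effect

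*Protocol*

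**What the plan says.** In the Research Proposal Summary (Experimental Design), Part I "explores the differences in clinical efficacy and reproductive outcomes between surgical and medical treatment for missed abortion". Section 4 repeats fertility outcome as an aim of Part I. The synopsis follow-up items include "the probability and outcome of subsequent pregnancies", and Section 5(6) specifies "Pregnancy rate after 1 year of trying to conceive (followed up every 6 months", followed by the outcomes of later pregnancies.

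Women choose between drug and surgical treatment and, in Part II, also choose their estrogen dose (Section 4, Grouping). The synopsis and Section 7 state only unadjusted tests: t-test, ANOVA, rank-sum, chi-square or Fisher.

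Two lists say what is recorded before treatment:
- The synopsis (Experimental procedure) has gestational age, symptoms, uterine and sac findings and HCG, then "parity, and whether there were other intrauterine diseases before pregnancy".
- Section 5(1) adds age and time of consultation, and ends with "number of previous intrauterine procedures, and whether there are other intrauterine diseases before pregnancy" and examples of such disease.

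Section 5(2) adds routine examinations, among them anti-Müllerian hormone (AMH) and thyroid function. The eligibility criteria do not exclude women with prior infertility or assisted conception.

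**The concern.** A woman's fecundity before the index pregnancy is likely to be a strong predictor of whether she conceives within a year of trying again. It could also influence her choice: a woman whose pregnancy was hard to achieve may weigh surgery, drugs or estrogen differently from one who conceived at once. A factor that predicts the outcome and may also drive the choice of group is a confounder.

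The protocol collects several items of reproductive history but not the ones closest to its own fertility outcome. If they are never collected, they cannot appear in a baseline table, be stratified on or enter a model, whatever a later analysis plan says. A gap in pregnancy rate between the groups would then have two explanations that the data cannot separate. What is at stake is the reproductive comparison. The short-term efficacy outcomes are largely unaffected.

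**Working it through.** **Is the gap in the documents?**

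| Item | Synopsis list | Section 5(1) | Section 5(2) | Eligibility |
|---|---|---|---|---|
| Prior infertility diagnosis | no | no | no | not excluded |
| Months to conceive the index pregnancy | no | no | no | – |
| Spontaneous or assisted conception | no | no | no | not excluded |
| Age | no | yes | – | 18-40 |
| Parity | yes | yes | – | – |
| Previous intrauterine procedures | no | yes | – | – |
| Intrauterine disease | yes | yes | – | – |
| AMH | no | no | yes | see objection |

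The items present are related to fertility, but they do not identify tubal, male-factor or unexplained infertility. A nulliparous woman with normal AMH may have conceived in one month or after years of treatment.

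**How large could the bias be?** The protocol has no figure to reproduce here. It gives no pregnancy rate and no prevalence of subfertility, and its 400 (Part I) and 180 (Part II) cases come without an effect size or power. The calculation below therefore rests on assumed inputs.

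Inputs:
- q, the share with prior subfertility: 10% in group 1; 10%, 20% or 30% in group 2 (assumed).
- f, the 1-year pregnancy rate without subfertility: 75% or 80% (assumed).
- s, the rate with subfertility: 40% or 50% (assumed).
- Treatment effect: zero.
- Test: two-sided at 5%. The protocol gives P < 0.05; two-sidedness is assumed.
- Group size: 200 v 200 (the 400 cases of Part I split equally, assumed) and 120 v 120 (if only some women try to conceive, assumed).

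Group rate: p = (1 − q)f + qs, so the spurious gap is (q₂ − q₁)(f − s).

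Rejection probability: 1 − Φ((1.96·SE₀ − gap)/SE₁) plus the negligible opposite tail. SE₀ = √(2p̄(1 − p̄)/n), where p̄ is the mean of the two rates, and SE₁ = √([p₁(1 − p₁) + p₂(1 − p₂)]/n).

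Worked case, q = 10% v 30%, f = 80%, s = 40%:
- p₁ = 0.9×0.80 + 0.1×0.40 = 0.76
- p₂ = 0.7×0.80 + 0.3×0.40 = 0.68
- gap = 0.08
- at n = 200, SE₀ = 0.0449 and SE₁ = 0.0447
- (1.96×0.0449 − 0.08)/0.0447 = 0.18, so the rejection probability is 43%.

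| q₁ v q₂ | f, s | p₁ v p₂ | Gap (points) | Rejection, 200 v 200 | Rejection, 120 v 120 |
|---|---|---|---|---|---|
| 10% v 10% | any | equal | 0 | 5% | 5% |
| 10% v 20% | 75%, 50% | 72.5% v 70.0% | 2.5 | 9% | 7% |
| 10% v 20% | 75%, 40% | 71.5% v 68.0% | 3.5 | 12% | 9% |
| 10% v 20% | 80%, 50% | 77.0% v 74.0% | 3 | 11% | 8% |
| 10% v 20% | 80%, 40% | 76.0% v 72.0% | 4 | 15% | 11% |
| 10% v 30% | 75%, 50% | 72.5% v 67.5% | 5 | 19% | 13% |
| 10% v 30% | 75%, 40% | 71.5% v 64.5% | 7 | 32% | 21% |
| 10% v 30% | 80%, 50% | 77.0% v 71.0% | 6 | 28% | 18% |
| 10% v 30% | 80%, 40% | 76.0% v 68.0% | 8 | 43% | 28% |

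With equal shares there is no bias. With unequal shares the gap does not shrink as the sample grows; a larger sample only makes it more likely to be declared significant.

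**The case against.** - **Bias is not certain.** A reader might infer that pre-existing subfertility will appear as a treatment effect. The documents do not support that: they give no prevalence, no direction and no evidence that the chosen groups differ in it. This stands. What remains is that a difference is possible and that the planned data could not reveal it.
- **Infertility is not said to result from treatment.** A reader might take the Background to name infertility as a complication of management. Its sentence, "This can cause complications such as endometrial damage, intrauterine adhesions, menstrual disorders, and infertility", refers to adherent tissue that was not expelled and is reported as a previous view. Of surgery, the Background says only that complications may affect later pregnancies. This stands. The point rests on the declared comparison of pregnancy rates, not on that sentence.
- **Partial cover exists.** Age, AMH, parity, previous procedures and intrauterine disease are recorded. Inclusion criterion ③ also requires normal routine examinations before treatment. If that includes AMH and thyroid function, some ovarian or endocrine subfertility is already excluded. This reduces the problem, but tubal, male-factor and unexplained infertility remain unseen.
- **The lists may not be exhaustive.** The synopsis list is introduced as a selection, and Section 5 is headed as key indicators. The actual data form could hold more. Even so, the fuller list names the neighbouring history items and omits these.
- **Adjustment may be left to an analysis plan that is not shown.** This is fair for the model, but such a plan cannot adjust for a variable that was not collected.
- **The rate counts only women trying to conceive.** That removes women not seeking pregnancy. It does not balance fecundity among those who are.

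**Conclusion.** The point holds in conditional form. A declared reproductive comparison between self-chosen groups lacks the baseline items most directly tied to its outcome. If subfertility is unequal between groups, the imbalance can be read as a treatment effect and cannot be checked or adjusted for. On the assumed values the spurious gap is 0 to 8 percentage points. False rejection is 5% to 43% at 200 v 200 and 5% to 28% at 120 v 120. The low end is no bias at all, and the direction is unknown. All prevalences, pregnancy rates and group splits are assumptions. The change is worth making because it is cheap. It matters most for Part I, whose stated aim names reproductive outcome, and it is easiest to apply in Part II.

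**What to change.** Add three items to Section 5(1) and to the synopsis list: mode of conception of the index pregnancy (spontaneous or assisted), months taken to conceive it, and any prior infertility diagnosis.

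- **Part II:** record them at enrolment, before the outcome is known.
- **Part I:** take them from chart entries made before treatment. A history asked for at the reproductive follow-up contact may be coloured by whether the woman has since conceived. Flag any such value and use it only in a sensitivity analysis.
- **Analysis:** compare the 1-year pregnancy rate adjusted for, or stratified by, these items together with age, AMH and parity. Report it also in spontaneously conceived index pregnancies alone. Collecting the items without an adjusted comparison would show an imbalance but not correct for it.

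The cost is three history items, one adjusted or stratified comparison, and some missing values in Part I, whose number should be reported by group. No treatment or visit changes.

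### The follow-up exclusion is not limited to the prospective part, so entry to the retrospective drug-versus-surgery comparison depends on what happened after treatment

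*Protocol*

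**What the plan says.** The Exclusion criteria in the Research Proposal Summary, repeated in section 4 (Research Content), form one list for both parts. The third item excludes "Those unable to follow up according to the follow-up plan". The Selection criteria in the Summary state the same rule separately for the retrospective and the prospective cohort: women "who met the inclusion criteria but did not meet the exclusion criteria were enrolled consecutively".

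The matching inclusion criterion is worded differently. The fifth item asks for "Good compliance, and follow-up observation as required (prospective study"), so it is limited to Part II. The exclusion carries no such limit.

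Section 5 (Key Evaluation Indicators) collects, among other outcomes:
- during drug treatment, "the time of expulsion of the gestational sac";
- at 3 months, "time of menstruation resumption";
- later, "Pregnancy rate after 1 year of trying to conceive (followed up every 6 months") and "spontaneous abortion rate, premature birth rate, full-term birth rate, stillbirth rate in subsequent pregnancies".

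For normally distributed measurements, section 7 (Statistical Analysis) says that "t-tests were used for comparisons between two groups, while ANOVA was used for comparisons among multiple groups". It names a rank-sum test for other measurements, and chi-square or Fisher tests for categories. The Summary names the t-test for quantitative data.

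**The concern.** An eligibility criterion should be decidable at or before treatment. In Part II a woman can be asked at consent whether she can attend. In Part I treatment is already past, so ability to follow up can be judged only from whether she came back. Her entry then depends on something that may itself be a result of the treatment or of its success.

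Part I compares drug with surgical treatment on efficacy and reproductive outcome, and women chose their own treatment. Return for follow-up could plausibly differ by treatment and by outcome. If it does, the retained women misrepresent each group. No later analysis can restore women who were never entered.

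A smaller concern is that a mean of observed times has no place for a woman without the event. Section 4 itself foresees non-expulsion and partial expulsion after medication.

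**Working it through.** **Step 1. Does the criterion reach Part I?** Three pieces of text, side by side:
- The exclusion list is shared, and its follow-up item has no limit to one part.
- The Selection criteria apply the list to the 2018–2023 cohort by name.
- The parallel inclusion item is limited to the prospective study, so the protocol makes that distinction where it intends it.

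As written, the criterion applies to Part I.

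**Step 2. Could it be a baseline judgement there?** Section 4 exempts Part I women from informed consent for data collection, so the protocol describes no point before treatment at which they could have been asked. The protocol is dated 21 November 2023, after the last Part I treatment (March 2023). In Part I the criterion can only act on follow-up that did or did not happen.

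**Step 3. How large could the bias be?** The protocol gives no loss rates, and it gives the 400 retrospective cases without inputs, so there is no plan figure to reproduce. The following is an illustration.

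Inputs: true success p = 81% (drug) and 96% (surgery), the background effectiveness rates in section 1. Assumed: a fraction ls of successes and a fraction lf of failures are not followed up and are therefore excluded.

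Observed success = p(1 − ls) / [p(1 − ls) + (1 − p)(1 − lf)]

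For p = 0.81:
- ls = lf = 10%: 0.729 / (0.729 + 0.171) = 81.0%
- ls = 10%, lf = 30%: 0.729 / (0.729 + 0.133) = 84.6%
- ls = 30%, lf = 10%: 0.567 / (0.567 + 0.171) = 76.8%

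For p = 0.96:
- ls = lf = 10%: 0.864 / (0.864 + 0.036) = 96.0%
- ls = 10%, lf = 30%: 0.864 / (0.864 + 0.028) = 96.9%
- ls = 30%, lf = 10%: 0.672 / (0.672 + 0.036) = 94.9%

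Effect on the comparison:

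| Loss pattern in both groups (successes/failures) | Drug | Surgery | Difference |
|---|---|---|---|
| 10% / 10% | 81.0% | 96.0% | 15.0 points |
| 10% / 30% | 84.6% | 96.9% | 12.3 points |
| 30% / 10% | 76.8% | 94.9% | 18.1 points |

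If both treatments truly succeed in 81% and loss depends on outcome in one group only, a difference appears from nothing: 84.6 − 81.0 = 3.6 points, or 81.0 − 76.8 = 4.2 points the other way.

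**Step 4. Event times.** A t-test or ANOVA needs a number for each woman. A woman who goes to surgery without expelling has no expulsion time. A woman whose menses have not returned at last contact has only a lower bound. A rank-sum test can include non-expellers, but only if a rule ranks them last, and the protocol states none. Expulsion time is listed under drug treatment only, so this point concerns comparisons within the drug-treated groups.

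**The case against.** The strongest reply is that the criterion was meant for Part II and its reach into Part I is a drafting slip. That may be so. But whoever abstracts the records will apply the list as written, and the slip is cheap to correct.

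A second reply is that women without follow-up have no late outcome, so nothing is lost by excluding them. That holds for the late outcomes only. Their treatment-time data (expulsion, operation time, blood loss, complications) would be discarded too, and loss could no longer be counted by group.

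A third reply is that handling of missing data may be in an analysis plan that is not shown. This is fair for the event times. The protocol names tests by data type, assigns none to a given outcome, and nowhere says that times are compared only in women who have the event. It does not excuse the exclusion, which is an eligibility rule fixed here.

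A reader might go further, and the documents do not support it:
- **That failures disappear from the study.** Retained tissue, curettage, and adhesions with their surgery and score are recorded, and chi-square tests can count them. Non-conceivers who are followed stay in the 1-year pregnancy rate.
- **That the worse treatment always looks better.** The direction depends on who is lost, and the documents do not say.
- **That Part II drop-outs are removed.** There the criterion reads naturally as eligibility at consent.
- **That expulsion time is biased between drug and surgery.** The surgical data list no such time.
- **That late Part I women lack a year of follow-up at the version date.** The version date is not a data cut-off.

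**Conclusion.** The point holds for Part I. As written, entry depends on a post-treatment event, which contradicts consecutive enrolment and can bias the main retrospective comparison. Under the assumed losses of 10% and 30%, a success rate of 81% moves by about 4 points either way, and a 15-point difference between treatments becomes 12.3 or 18.1. With loss unrelated to outcome there is no bias in the rates. These sizes rest wholly on assumed losses and on background rates borrowed for illustration. They show what is possible and do not estimate what happened.

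The event-time point is secondary: the mean-based tests named do not fit outcomes that some women will not have. The per-pregnancy definition of the birth outcomes is explicit and is not an error.

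**What to change.** - **Part I:** delete the follow-up exclusion. Enter every eligible treated woman and keep her in the denominator.
- **Part II:** reword it as a judgement made at consent, in line with the fifth inclusion criterion, and say that women lost later remain enrolled.
- **Both parts:** report loss to follow-up by treatment group, with a sensitivity analysis over plausible outcomes for the women lost.
- **Time to sac expulsion (within drug-treated groups):** replace the t-test or ANOVA on observed times with cumulative incidence, counting surgery before expulsion as a competing event, or with a rank-sum test that ranks non-expellers last.
- **Time to return of menses:** use Kaplan–Meier with censoring at last contact.

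The cost is a change of wording and the use of dates that the protocol already plans to collect or that stand in the records. Some women will contribute partial data, so intervals widen slightly.
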